7.3.2.7.4. Visit 1: 0-10 days post-Surgery

Data collection 10 days or less post-insertion and after-effects of anaesthesia have worn off:

- Health Survey (HS): complete prior to impedance measurements.
- Impedance (MP1+2 and Four point).
- High Resolution CT: Post-operative imaging within 3 months (before end of Visit 4 window) to assess electrode placement. Cone beam CT and flat panel CT are examples. Not applicable if completed intraoperatively.

7.3.2.7.5. Visit 2: 15 Days post-Surgery / Activation (±7 days)

- Health Survey (HS): complete prior to impedance measurements.
- Blinding Questionnaire.
- Impedance (MP1+2 and Four point): measured two times:
 - \circ Before activation.
 - After activation and mapping is complete.
- Cochlear Implant Activation with selected sound processor.
- CI optimisation / Mapping.
- High Resolution CT: Post-operative imaging within 3 months (before end of Visit 4 window) to assess electrode placement. Cone beam CT and flat panel CT are examples. Not applicable if completed intraoperatively.

7.3.2.7.6. Visit 3: 30 days after Visit 2 (±5 days)

Thirty days after the IMD/comparator is activated, the following should be completed:

- Audiogram
- Health Utilisation Index III
- Dizziness/Tinnitus Questionnaire (DTQ)
- Dizziness Handicap Inventory (DHI)
- Tinnitus Handicap Inventory (THI)
- Health Survey: complete before impedance measurements
- Impedance (MP1+2 and Four point) (complete before CI optimisation / Mapping)
- CI optimisation / Mapping
- Battery Life Estimation Test with 900Hz/channel and 8 max. (as required) (complete after CI optimisation / Mapping)
- High Resolution CT: Post-operative imaging within 3 months (before end of Visit 4 window) to assess electrode placement. Cone beam CT and flat panel CT are examples. Not applicable if completed intraoperatively.

7.3.2.7.7. Visit 4: 3 Months post-Surgery (90 days, ±14 days)

- Audiogram
- Health Utilisation Index III
- Dizziness/Tinnitus Questionnaire (DTQ)
- Dizziness Handicap Inventory (DHI)
- Tinnitus Handicap Inventory (THI)
- Health Survey: complete before impedance measurements
- Speech Perception Testing
- Impedance (MP1+2 and Four point) (complete before CI optimisation / Mapping)
- CI optimisation / Mapping
- Battery Life Estimation Test with 900Hz/channel and 8 maxima. (as required) (complete after CI optimisation / Mapping)
- High Resolution CT: Post-operative imaging within 3 months (before end of Visit 4 window) to assess electrode placement. Cone beam CT and flat panel CT are examples. Not applicable if completed intraoperatively.
- 7.3.2.7.8. Visit 5: 6 Months post-Surgery (180 days, +14 days)
 - Audiogram
 - Health Utilisation Index III

- Dizziness/Tinnitus Questionnaire (DTQ)
- Dizziness Handicap Inventory (DHI)
- Tinnitus Handicap Inventory (THI)
- Health Survey: complete before impedance measurements.
- Blinding Questionnaire
- Speech Perception Testing
- Impedance (MP1+2 and Four point) (complete before CI optimisation / Mapping)
- CI optimisation / Mapping
- Battery Life Estimation Test with 900Hz/channel and 8 max. (as required) (complete after CI optimisation / Mapping)
- 7.3.2.7.9. Visit 6: 9 Month post-Surgery (270 days, ±30 days)
 - Audiogram
 - Dizziness/Tinnitus Questionnaire (DTQ)
 - Dizziness Handicap Inventory: Should be completed in accordance with DTQ.
 - Tinnitus Handicap Inventory: Should be completed in accordance with DTQ.
 - Health Survey: complete before impedance measurements.
 - Impedance (MP1+2 and Four point) (complete before CI optimisation / Mapping)
 - Cl optimisation / Mapping
 - Battery Life Estimation Test with 900Hz/channel and 8 max. (as required) (complete after CI optimisation / Mapping).

7.3.2.7.10. Visit 7: 12 Month post-Surgery (365 days, +30 days)

- Audiogram
- Health Utilisation Index III
- Dizziness/Tinnitus Questionnaire (DTQ)
- Dizziness Handicap Inventory (DHI)
- Tinnitus Handicap Inventory (THI)
- Health Survey: complete before impedance measurements.
- Speech Perception Testing
- Impedance (MP1+2 and Four point) (complete before CI optimisation / Mapping)
- CI optimisation / Mapping
- Battery Life Estimation Test with 900Hz/channel and 8 max. (as required) (complete after CI optimisation / Mapping).

7.3.2.7.11. End-of-Study

Document reason for Subject's study completion. Ensure device deficiencies, device exposure, adverse events, concomitant medication and deviations are reviewed, and end dates recorded where appropriate.

7.3.2.8. Collected from point of Consent

- Concomitant Medication: includes all prescription medications, routine over-the counter medications, and any use of steroids. Concomitant medications should be reviewed at each visit.
- Protocol Deviations: approved and unapproved deviations

7.3.2.9. Collected from point of Randomisation

• Adverse Events and review of ongoing adverse events. Adverse events should be reviewed at each visit.

7.3.2.10. Collected from point of Surgery

- Device Exposure
- Device Deficiency

7.3.2.11. Remote Programming

Cochlear[™]'s Remote Programming tool may be used as an alternative data collection option, should a subject not be able to return to clinic due to the impact of the COVID-19 pandemic at Visit 3, Visit 4, Visit 5, Visit 6 and Visit 7. Equipment (which may include laptop, pod, virtual machine, sound processor cables and N6 Sound Processor) will be mailed to subject by the clinic to complete the impedance testing. The subjects own N7 Sound Processor may be used as well. After testing is completed, the subject mails the equipment back to the clinic.

The following assessments may be completed with Remote Programming:

- Impedance (MP1+2 and four point) (complete before CI optimisation / Mapping)
- Cl optimisation / Mapping
- Battery Life Estimation Test with 900Hz/channel and 8 max. (as required) (complete after CI optimisation / testing)

Use of Remote Programming will be recorded in the eCRF. Protocol deviations are required to be entered if the subject cannot attend the clinic for other assessments.

7.3.2.12. Electrical Testing

Electrocochleography (ECochG) is permitted outside of the clinical investigation. ECochG and other cochlear implant electrical testing not specified within this clinical investigation plan must be completed after clinical investigation required electrical testing (e.g. impedance or NRT).

7.3.3 Safety Evaluations and Procedures

The risks and anticipated ADEs for the CI632D and CI632, as identified in Sections 8.2 and 8.3 of the CIP, will be assessed in the clinical investigation via reporting of all AEs/ADEs from the time of first subject randomisation until last subject last visit. Individual collection of adverse events will end when the subject exits the clinical investigation. Safety data review will be conducted by the Sponsor's Safety Officer in accordance with the Sponsor's standard operating procedures.

Safety data review will be conducted by an Independent Data Monitoring Committee (IDMC) in accordance with the defined Charter for operations.

Upon review of data available in the CRF, the Sponsor or IDMC may query data or request de-identified source documents to review the event.

7.3.3.1. Concomitant Medication and Therapies

Concomitant Medications recorded in the CRF includes all prescription medications, routine over-the counter medications, and any use of steroids. Dexamethasone cannot be delivered into the ear or used to treat the electrode (Section 7.3.1.). There are no further prohibited medications under this clinical investigation. Medications taken for anaesthesia purposes during surgery will not be recorded unless their use deviates from normal clinical practice.

7.4. Equipment Used for Evaluations and Procedures

The clinical investigation includes use of equipment to complete assessments. Equipment including software, firmware, sound equipment (e.g. speakers) are used to assess impedance measurements and speech perception performance. Software and firmware should be kept current at the direction of the Sponsor. Versions of applicable software and firmware used for each subject assessment should be documented. For equipment used in this clinical investigation, records of equipment calibration requirements and the calibration records must be maintained in site files and copies provided to the Sponsor. As part of the Site Initiation Visit, requirements and records should be provided to the Sponsor and records to be confirmed to be up-to-date. Records will be monitored at interim monitoring visits, in accordance with the Sponsor's Monitoring Plan.

Custom Sound[®] and Custom Sound[®] EP software or the latest Cochlear software platform for advanced objective measurements, will be used to measure MP1+2 impedances, four point impedances and other collected data points. Four point impedances will be measured during stimulation of two intracochlear electrodes while measuring impedances on two separate intracochlear electrodes. Measurement of four point impedances with Custom Sound EP software allows assessment of tissue impedance without measuring the impedance of the interface and aims to provide information about fibrous tissue growth around the electrode array. Upload of all Custom Sound data to Sponsor database for analysis is required, which may be done automatically or manual file sharing.

The Sponsor may provide equipment to utilise Remote Programming should the COVID-19 pandemic impact a subject's ability to visit the clinic. Equipment (may include laptop, pod, virtual machine, sound processor cables and N6 Sound Processor) will be mailed to subject by the clinic to complete the impedance testing and

returned after the visit. The use of equipment will be logged and reviewed as per the Sponsor's Monitoring Plan.

Speech perception performance in quiet for monosyllabic word and sentence lists will be assessed using a loudspeaker configuration with the signal from the front, zero Azimuth (S_0) at head height and 1 metre distance. The Sponsor may provide equipment (such as laptop, software, microphone and speaker) if the clinical site does not have it available.

7.5. Sponsor Role in Conduct of the Clinical Investigation

The Sponsor may support certain activities at the clinical investigation site. Sponsor representatives may be present in the operating room with the surgical team and subject. The representative will not provide medical assistance and will not discuss the trial with the subject. During the surgery or during study visits, the sponsor representative may assist in completing the electrical testing of the cochlear implant.

The Sponsor may pay for third party clinical trial support ("coordinator") at clinical investigation sites should there be resource constraints, which may support subject recruitment, data entry and reporting under the authority of the Principal Investigator. The coordinator will be required to comply with hospital policy and will be trained on the CIP and GCP. The coordinator will not complete any activities on behalf of the Sponsor.

An independent Sponsor representative will review evidence of subject eligibility before the subject is accepted for randomisation. This representative will not work in any other capacity of the clinical investigation and will be trained on the CIP and GCP.

8. BENEFITS AND RISKS OF THE INVESTIGATIONAL MEDICAL DEVICE AND CLINICAL INVESTIGATION

8.1 Anticipated Clinical Benefits

The anticipated clinical benefits include the benefits associated with the CI632, as described in the Physician's Guide. Benefits may include:

- detection of medium to loud environmental sounds at comfortable listening levels.
- detection of conversational speech at comfortable listening levels.
- limited improvement in the recognition of environmental sounds.
- limited ability to use the telephone.
- improvement in speech recognition in a quiet environment in the implanted ear.
- improvement in speech recognition in a noisy environment.
- improvement in overall sound quality.

- reduced tinnitus.
- reduced fatigue when listening.

The additional potential clinical benefits of the CI632D relate to release of therapeutic dose of dexamethasone into the cochlea over a period of 30 days. This is anticipated to aid in minimising the inflammatory response to electrode insertion. Possible benefits could include:

- Reduced formation of fibrosis within the cochlea, as measured by decreased electrical impedance.
- Reduced electrode electrical impedance, possibly resulting in improved sound processor battery life.

The clinical investigation may require more appointments than standard of care. Study subjects may receive benefit from extra medical attention.

8.2 Anticipated Adverse Device Effects

Prospective recipients should be advised of the following possible effects of receiving a cochlear implant, as described in the CI632 Physicians Guide:

Adverse effects

- Normal risks associated with surgery and general anaesthesia.
- Increased surgical and anaesthetic risks for certain populations.
- Complications most frequently associated with this surgical procedure—stimulation of the facial nerve, taste disturbance and tinnitus.
- Complications that may require additional medical treatment, surgery and/or removal of the device, such as:
 - Acute Otitis Media (AOM)
 - facial nerve injury leading to temporary facial nerve weakness
 - perilymph fistula
 - Concurrent Cerebrospinal Fluid (CSF) leakage
 - vestibular dysfunction
 - subdural injury
 - subcutaneous haematoma
 - irritation, inflammation or breakdown of the skin flap; infection; and in some cases, extrusion
 of the device caused by the presence of a foreign body under the skin
 - decreased hearing ability caused by the electrode array migrating partially or completely out of the cochlea
 - perforation of external ear structures, such as the tympanic membrane or canal wall, by the electrode lead

- perception of non-auditory sensations and poorer performance than expected from misplacement of the electrode array
- Electrical stimulation may result in increased tinnitus, temporary facial nerve stimulation, temporary dizziness, or temporary pain
- The long-term effects of electrode insertion trauma or chronic electrical stimulation are unknown. Such effects may include new bone growth in the cochlea or deterioration of the nerve cells. These effects may preclude replacement of the electrode array or may lead to eventual deterioration of cochlear response.
- Failure of component parts (both external and internal) could result in the perception of an uncomfortably loud sound sensation, intermittent sound, or no sound.
- Failure of various component parts of the implanted device could require removal or replacement of the implant, or a reduction in the number of electrodes used.

Meningitis

- Before implantation, candidates should consult their primary care physician and implanting surgeon regarding vaccination status against micro-organisms that cause meningitis.
- Meningitis is a known risk of inner ear surgery and candidates should be appropriately counselled of this risk. Certain preoperative conditions may increase the risk of meningitis with or without an implant. These conditions include:
 - Mondini's syndrome and other congenital cochlear malformations.
 - CSF shunts or drains.
 - recurrent episodes of bacterial meningitis before implantation.
 - perilymph fistulas and skull fracture/defect with CSF communication.

Loss of residual hearing

Inserting the electrode into the cochlea may result in complete loss of residual hearing in the implanted ear.

8.3 Risks Associated with Participation in the Clinical Investigation

The surgical procedure may result in adverse effects, as described in the Investigators Brochure for CI632D. The risks for undergoing the cochlear implant surgery are the same as the risks if not participating in the clinical investigation. If the subject is randomised to the IMD arm, there may be risks associated with the dexamethasone delivered via the cochlear implant. The likelihood of experiencing these risks is minimal given the small amount of dexamethasone that will be eluted.

The clinical investigation may include some inconveniences to the subject as the number of follow-up visits may be more than if the subject was not participating. Follow-up visits may be longer in duration than a routine cochlear implant follow-up. Some of the required assessments and exams may result in discomfort for the subject. Subjects may feel discomfort during the process of identifying the most appropriate program settings.

8.3.1 Risks specifically associated with the CI632D

The additional risks associated with the use of the investigational dexamethasone-eluting electrode array have been assessed. One residual risk has been identified as a "High" risk and relates to the possibility that introduction of the therapeutic substance may adversely affect local immunity, leading to an increased risk of infection.

However, the hazards analysis indicates that the residual likelihood of infection is not expected to be any higher than the residual likelihood of meningitis and other central nervous system infections for the CI632 and therefore a residual likelihood of 'remote' has been assigned. Together with the severity of "catastrophic', this results in a residual risk that is rated "High".

Other residual risks related to the presence of dexamethasone, including the risks related to long-term presence of the implant in the body, variation in drug release, instability or interactions with other drugs have been assigned residual likelihoods of "remote" or "improbable", with a risk level of "medium".

8.4 Risk Mitigation

- All surgeons will receive surgical training in the use and handling of the CI632 and CI632D as part of study initiation. In addition, the Sponsor's surgical support may be present during surgeries performed by the investigational site(s). There is no difference to the implant technique or device handling between CI632 and CI632D.
- All reported AEs, ADEs and DDs will be regularly reviewed by the Sponsor's Clinical review Board for the duration of the study to facilitate early detection and appropriate intervention if events are unanticipated with respect to incidence, severity, or outcome.
- An Independent Data Monitoring Committee (IDMC) will review all SADEs and infection-related AEs for the duration of the study to facilitate early detection and appropriate intervention if events are unanticipated with respect to incidence, severity, or outcome.
- Inclusion in the study requires evidence of pneumococcal vaccination prior to randomisation.
- Defined eligibility criteria to address preoperative conditions that may increase risk of meningitis.

8.5 Benefit-to Risk Rationale

Benefits of a cochlear implant to the recipient may include improved detection and recognition of environmental sounds, improved detection and recognition of conversational speech, limited ability to use the telephone and overall improvement in sound quality. The clinical safety (risks) and benefit relevant to the anticipated performance of CI600-series devices, including CI632, were evaluated in the CI600 series Clinical Evaluation Report (CER) and it was concluded that the device is effective and has a favourable safety profile. The CI600 series cochlear implants are commercially available in multiple countries. Cochlear™-sponsored clinical investigations and a systematic literature review, coupled with the design verification/validation and post-market surveillance data, established that the benefits of the CI600-series devices outweigh the risks.

The anticipated additional benefits of dexamethasone, compared with a conventional CI electrode, that will be investigated in this study are reduced fibrosis in the cochlea as measured by electrode impedances, and

improved battery life due to reduced power consumption for stimulation. The additional risks that may be posed by the dexamethasone-eluting electrode incorporated into the CI632D have been assessed and do not alter the conclusion that the potential benefits outweigh the risks for the investigational device.

It is anticipated speech outcomes for CI632D will be non-inferior to CI632.

Delivery of dexamethasone to the middle and inner ear via intratympanic or transtympanic injection, or application to the round window is widely used and accepted in cochlear implant surgery (see Section 4.2.2.1) and delivery of dexamethasone via the round window is included in the FDA-approved recommended hearing preservation surgery technique for Med-El cochlear implants

(https://www.accessdata.fda.gov/cdrh_docs/pdf/P000025S084c.pdf). Intratympanic delivery of dexamethasone has been shown to result in highly localized delivery of a relatively small quantity of drug with much lower systemic concentrations than intravenous delivery (Bird et al., 2011). Consequently, the risks of systemic side-effects are reduced. The total quantity of dexamethasone incorporated into the CI632D is approximately 15 to 110-fold smaller than the quantities used for local application in the studies referred to in Section 4.2.2.1, further reducing the risk of adverse effects.

9. STATISTICAL CONSIDERATIONS

9.1. General Considerations

A detailed summary of statistical analysis is documented in the Statistical Analysis Plan (SAP).

9.2. Endpoints

9.2.1. Primary Endpoints

- 1. Difference between CI632D and CI632 mean MP1+2 impedance measurements of the available electrodes at 6 months post-cochlear implantation.
- 2. Difference between CI632D mean speech perception performance for open-set monosyllabic word recognition in quiet in the unilateral listening condition at six months post-implant compared to preoperative baseline.

9.2.2. Secondary Endpoints

- 1. Comparison of CI632D and CI632 procedural and device related adverse events at 6 Months and 12 Months post-cochlear implant.
- 2. Difference between CI632D and CI632 mean speech perception performance for an open-set monosyllabic word recognition in quiet in the unilateral listening condition at six months post-cochlear implant.
- 3. Difference between CI632D and CI632 mean speech perception performance for sentence recognition in quiet in the unilateral listening condition at six months post-cochlear implant.
- 4. Comparison of CI632D and CI632 Custom Sound[®] estimated remaining battery life of the sound processor at all data collection time points.

Clinical Investigation Plan | Approval Date (GMT+

13.0

9.3. Hypotheses

9.3.1. Primary Hypothesis

9.3.1.1. Primary Endpoint #1

Mean MP1+2 impedance will be significantly lower with the CI632D ("treatment" arm) than the standard CI632 ("control" arm) 6 months post-implant.

H0: MP1+2_{treatment} \geq MP1+2_{control}

H1: MP1+2_{treatment} < MP1+2_{control}

9.3.1.2. Primary Endpoint #2

Mean CNC word score in quiet will show at least 10% improvement with the Cl632D ("treatment" arm) at 6 months post-implant compared to "treatment" arm's preoperative Baseline, is as follows:

H0: CI632D CNC word_{6 Month} < CI632D CNC word_{Baseline} + 10%

H1: CI632D CNC word_{6 Month} \geq CI632D CNC word_{Baseline} +10%

9.3.2. Secondary Hypothesis

Three secondary endpoints are planned; one related to adverse events and two related to mean change in speech perception performance.

Analyses of secondary endpoints, as well as other assessments, will be performed but there are no plans for formal prespecified hypothesis tests for these analyses with type I error control. It is recognized that this may limit the ability for such analyses to support labelling claims with inferential quantities.

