7.3.2.3. Description of Speech Perception Testing

The following speech perception testing will be completed during the clinical investigation:

1. Two lists of CNC words at 60 dBA in quiet delivered from a speaker located directly in front of the listener (S0):

- Screening/Baseline testing scenarios:
 - i. Each ear in the aided condition, with the contralateral ear plugged.
 - ii. Both ears together in the aided condition.
- Post-operative:
 - i. Unilateral: Cochlear implant^p with the contralateral ear plugged.
 - ii. Bimodal: Cochlear implant^p with a hearing aid in contralateral ear.
- 2. One list of AzBio sentences at 60 dBA in guiet delivered from a speaker located directly in front of the listener (SO):
 - Screening/Baseline testing scenarios:
 - i. Each ear in the aided condition, with the contralateral ear plugged.
 - ii. Both ears together in the aided condition.
 - Post-operative:
 - i. Unilateral: Cochlear implant^p with the contralateral ear plugged.
 - ii. Bimodal: Cochlear implant^p with a hearing aid in contralateral ear.

The American AzBio sentences are recorded in Australian and New Zealand accents for use at Australian and New Zealand sites.

In the United States, contralateral hearing aids may be provided to subjects should their own hearing aid not provide optimal therapy.

7.3.2.4. **Description of Battery Life Estimation Test**

Measuring projected sound processor battery life will be completed during the clinical investigation on the ear with CI632/CI632D.

Impedance Measurements 7.3.2.5.

Four point impedance measurements are measured using Custom Sound® EP software or the latest Cochlear software platform for advanced objective measurements. The four point impedance measurement is an investigational measurement and therefore requires a research key in order to activate this measurement in

^p Some individuals will make use of the ipsilateral acoustic component to augment the cochlear implant and as a result allow access to Hybrid stimulation. In these cases, "Cochlear implant" would correspond to Hybrid (i.e., cochlear implant

⁺ hearing aid in the same ear).

Custom Sound EP. FDA reviewed the four point impedance measurement during the IDE review of G200098. The Sponsor may provide a laptop to use this software during the cochlear implant operation and at study visits. A CP910/CP920 sound processor will be used when testing with Custom Sound EP at all study visits.

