9.6.2. Secondary Endpoint Analyses

See Section 9.7 for Safety Analysis under the secondary endpoint. There are two speech perception endpoints at six months post-implantation. There are no formal statistical hypothesis planned for these endpoints; analyses will be based on descriptive statistics and nominal 95% confidence limits, with results reported separately by randomized group. The ITT population will be used for primary analysis for each endpoint. A secondary analysis will include the Per Protocol group. Missing data will be analysed under a multiple imputation strategy that will be outlined in the Statistical Analysis Plan (SAP). Analysis of estimated remaining battery life of Cl632D and Cl632 Custom Sound[®] will be conducted.

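### Section 9.3.2 miscounts the secondary endpoints and calls the two speech endpoints change scores, while 9.6.2 gives no interval for the between-arm difference that 9.2.2 defines and makes no use of the preoperative score

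*Protocol*

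**What the plan says.** Protocol section 9.3.2 states that three secondary endpoints are planned: "one related to adverse events and two related to mean change in speech perception performance". It adds that none of them carries a formal test with type I error control.

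Section 9.2.2 lists four. Number 1 is adverse events and number 4 is estimated remaining battery life. Numbers 2 and 3 are between-arm differences, CI632D against CI632, in "mean speech perception performance for an open-set monosyllabic word recognition in quiet in the unilateral listening condition at six months post-cochlear implant" and in "mean speech perception performance for sentence recognition in quiet in the unilateral listening condition at six months post-cochlear implant". Neither mentions baseline. The synopsis has the same four, defined the same way.

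Section 9.6.2 says "There are two speech perception endpoints at six months post-implantation" and that "analyses will be based on descriptive statistics and nominal 95% confidence limits", with results given for each randomised group on its own. It names no covariate. It also provides for an analysis of battery life, so it agrees with a count of four.

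The preoperative scores exist. Section 7.3.2.3 has CNC words and AzBio sentences tested at baseline as follows: "Each ear in the aided condition, with the contralateral ear plugged". The Schedule of Events requires this testing within 90 days before randomisation.

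**The concern.** The two speech endpoints are described in two ways. A change from baseline and a six-month score are different summaries with different variances, and an analyst following 9.3.2 would compute something other than an analyst following 9.2.2. A SAP that adopts either one departs from a section of the protocol.

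The reporting plan also stops short of the endpoint. Section 9.2.2 defines a difference between arms, but 9.6.2 promises limits only within each arm. These endpoints carry the speech half of the secondary objective (section 6.2), that CI632D is similar to the standard electrode, and section 8.5 anticipates non-inferior speech outcomes. With no formal test, the estimated difference and its interval are the natural evidence on similarity, and the plan does not ask for them.

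Finally, a pre-randomisation score for the same test in the same ear is collected at no extra cost and is not brought into the comparison.

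**Working it through.** **Comparing the sections.**

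| Place | Number of secondary endpoints | Speech endpoints |
|---|---|---|
| Synopsis | four | between-arm difference in mean at six months |
| 9.2.2 | four | between-arm difference in mean at six months |
| 9.3.2 | three | mean change |
| 9.6.2 | safety, two speech, battery life | six months, summarised by arm |

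Section 9.3.2 is the odd one out on both columns. Elsewhere, when the protocol intends a baseline comparison for speech, it says so. Primary endpoint 2 (section 9.2.1) is measured "in the unilateral listening condition at six months post-implant compared to preoperative baseline".

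**What the choice does to precision.** The protocol states no sample size, power or margin for these endpoints, so there is no figure of its own to reproduce.

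Inputs:
- SD of CNC change, 22.6, from section 9.4 (predicate-device study, 96 subjects), read here as percentage points.
- 60 per arm, the maximum in section 7.1.
- Baseline SD, 12. This is an assumption; the protocol gives none.
- Correlation rho between baseline and six-month score, 0.2 or 0.5. Also an assumption.

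Formulas:
- 95% half-width of the difference = 1.96 × SD × √(2/60) = 0.358 × SD.
- The six-month SD, s, follows from 22.6² = s² + 12² − 2 × rho × 12 × s. Hence s = 12 × rho + √((12 × rho)² − 12² + 22.6²).
- The adjusted (ANCOVA) SD is s × √(1 − rho²), ignoring the one degree of freedom spent on the covariate.

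At rho 0.2: s = 2.4 + √(5.76 + 366.76) = 21.7, and the adjusted SD is 21.7 × 0.980 = 21.3.

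At rho 0.5: s = 6 + √(36 + 366.76) = 26.1, and the adjusted SD is 26.1 × 0.866 = 22.6.

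| rho | Raw six-month score | Change | Adjusted |
|---|---|---|---|
| 0.2 | 7.8 | 8.1 | 7.6 |
| 0.5 | 9.3 | 8.1 | 8.1 |

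The order of raw and change reverses between the two rows, so the protocol's figures cannot say which is tighter. Adjustment is no wider than either. Over a broader assumed range (baseline SD 8 to 15, rho 0 to 0.6), the raw half-width runs from 6.0 to 10.1 and the adjusted one from 6.0 to 8.1, with change fixed at 8.1.

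**Why limits by arm do not stand in for the difference.** With SD 22.6 and 60 per arm, each arm's half-width is 1.96 × 22.6 / √60 = 5.7. Two such intervals just touch when the means differ by 5.7 + 5.7 = 11.4 points, whereas the interval for the difference has half-width 8.1. Judging similarity by overlap would be too lenient.

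**The case against.** The best defence has four parts.

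First, the change wording may be loose usage rather than a second definition. Section 9.4 refers to the 1.5 kOhm difference between arms as a change, with no baseline involved, and 9.2.2 and the synopsis agree with each other. That is plausible. It makes the correction editorial, but it does not remove the conflicting text or explain the count of three.

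Second, covariates are commonly left to the SAP, and sections 9.1 and 9.5 point there. This stands: the absence of ANCOVA is an opportunity, not an error. However, 9.6.2 itself fixes the form of the analysis, descriptive and by arm, and defers only missing data to the SAP.

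Third, the consequence is limited. No formal test is attached, and section 9.3.2 acknowledges that this may restrict labelling claims. This also stands.

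Fourth, the gain may be small. The entry criterion caps the baseline word score at 40% in the ear to be implanted, and such a restricted range may limit the correlation.

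A reader might infer more than the documents support:
- That neither definition accounts for baseline. A change score subtracts it; only regression adjustment is absent.
- That the protocol prescribes an unadjusted analysis. It says no such thing; it merely names no covariate.
- That the comparison is biased. Under randomisation the raw, change and adjusted contrasts all estimate the same between-arm difference.
- That adjustment is worth 10% to 33% more subjects. That is 1/(1 − rho²) at an assumed rho of 0.3 to 0.5, measured against the raw score only. Half-widths quoted with it would also need 22.6, an SD of change, to serve as the six-month SD.
- That the definition is open to choice after the results are seen. The endpoint is stated consistently in two places and the SAP is not at hand.

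**Conclusion.** The point holds as an inconsistency with an inexpensive improvement attached. Section 9.3.2 is wrong on the number of secondary endpoints and describes the speech endpoints differently from 9.2.2 and the synopsis. Section 9.6.2, as written, does not deliver an interval for the difference that 9.2.2 defines, and it leaves the same-ear preoperative score unused.

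The gain from repairing this is one consistent definition and some precision. Its size is unknown. At 60 per arm, with the assumed baseline SD of 12, adjustment narrows the raw half-width by about 0.2 points at rho 0.2 and by about 1.2 to 1.3 points at rho 0.5. Against the change score it gains about 0.5 points at rho 0.2 and essentially nothing at rho 0.5. These figures rest on 22.6 carrying over to this trial as the SD of change and on the assumed baseline SD and correlation. They concern CNC words only, since the protocol gives no SD for AzBio sentences.

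**What to change.** In section 9.3.2, state four secondary endpoints, adding battery life, and remove the description of the speech endpoints as mean change so that it matches 9.2.2 and the synopsis.

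In section 9.6.2, specify that secondary endpoints 2 and 3 are each estimated as the CI632D minus CI632 difference at six months, from an ANCOVA with treatment and the preoperative score of the same test in the implanted ear, with a nominal 95% confidence interval. The summaries by arm can stay alongside.

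The cost is a few lines of text and one covariate. No new data are needed, and because these endpoints carry no formal test there is no alpha consequence.
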